4.2.7.5 Additional Analyses of Secondary Endpoint

No additional analysis.

4.2.7.6 Subgroup Analyses of Secondary Endpoint

The analysis described in Section 4.2.7.4 is repeated in subgroups described in Section 4.2.1.7.

4.2.7.7 Interim Analysis of Secondary Endpoint

The derivation of baseline, post-baseline and change from baseline in daily maintenance OCS dose is described in Section 4.2.7.2.

The absolute values as well as absolute and percentage change from baseline in daily maintenance OCS dose are presented over time on the FAS.

4.2.8 Secondary Endpoint - Change from baseline in post-BD FEV₁ at Week 28 and Week 52.

4.2.8.1 Definition

The change from baseline in post-bronchodilator FEV₁ is calculated at Week 28 and Week 52.

4.2.8.2 Derivations

The absolute change from baseline in post-BD FEV1 at a post-baseline visit is calculated as described in Section 3.3 on the FAS. Baseline value is derived as presented in Section 3.3.1.2. Strategies of handling intercurrent events are presented in Section 4.2.

4.2.8.3 Handling of Dropouts and Missing Data

No data imputation.

4.2.8.4 Primary Analysis of Secondary Endpoint

The absolute values and absolute changes from baseline in post-BD FEV1 are summarised using descriptive statistics over time. All data available at primary DBL is presented, which includes data beyond Week 28 (see Section 3.1).

The same statistical analysis as described in Section 4.2.7.4 is applied for the absolute change from baseline in post-BD FEV1. The baseline of post-BD FEV1 is used as covariate instead of the baseline OCS dose.

The analyses are performed based on the FAS.

4.2.8.5 Additional Analyses of Secondary Endpoint

No additional analysis

4.2.8.6 Subgroup Analyses of Secondary Endpoint

The analysis described in Section 4.2.8.4 is repeated in subgroups described in Section 4.2.1.7.

4.2.8.7 Interim Analysis of Secondary Endpoint

The absolute values and absolute changes from baseline in post-BD FEV1, derived as described in Section 4.2.8.2, are presented over time on the FAS.

4.2.9 Secondary Endpoint - Change from baseline in Asthma Control Questionnaire 6 (ACQ-6) at Week 28 and Week 52

4.2.9.1 Definition

The ACQ-6 questionnaire includes the following questions:

- 1. Awakening at night by symptoms
- 2. Limitations of normal daily activities
- 3. Waking in the morning with symptoms
- 4. Dyspnoea
- 5. Wheeze
- 6. Daily rescue medication

The questions of the ACQ-6 are measured on a 7-point scale scored from 0 (totally controlled) to 6 (severely uncontrolled).

This endpoint is the change from baseline in Asthma Control Questionnaire 6 (ACQ-6) at Week 28 and Week 52.

4.2.9.2 **Derivations**

The ACQ-6 score is computed as the unweighted mean of the responses to the 6 questions presented above. Higher scores indicate poorer outcomes. If response to any of the questions is missing, the ACQ-6 is automatically set to missing (directly managed at the data entry level).

The absolute change from baseline in Asthma Control Questionnaire 6 (ACQ-6) score at a post-baseline visit is calculated for participants on the FAS as described in Section 3.3. Baseline value is derived as presented in Section 3.3.1.2. Strategies of handling intercurrent events are presented in Section 4.2.

4.2.9.3 Handling of Dropouts and Missing Data

No data imputation.

4.2.9.4 Primary Analysis of Secondary Endpoint

The absolute values and absolute changes from baseline in ACQ-6 score are summarised using descriptive statistics over time. All data available at primary DBL is presented, which includes data beyond Week 28 (see Section 3.1).

The same statistical analysis as described in Section 4.2.7.4 is applied for the absolute change from baseline in ACQ-6 score except that the visit covariate is replaced by weekly timepoints and the baseline of ACQ-6 is used as covariate instead of the baseline OCS.

The analyses are performed based on the FAS.

4.2.9.5 Additional Analyses of Secondary Endpoint

No additional analysis.

4.2.9.6 Subgroup Analyses of Secondary Endpoint

The analysis described in Section 4.2.9.4 is repeated in subgroups described in Section 4.2.1.7.

4.2.9.7 Interim Analysis of Secondary Endpoint

The absolute values and changes from baseline in ACQ-6 score, derived as described in Section 4.2.9.2, are presented over time on the FAS.

4.2.10 Secondary Endpoint - Change from baseline in standardised Asthma Quality of Life Questionnaire for 12 years and older (AQLQ[s]+12) total score at Week 28 and Week 52

4.2.10.1 Definition

In the AQLQ(S) +12 the participants are asked to recall their experiences during the previous 2 weeks and to score each of the 32 questions on a 7-point scale ranging from 7 (no impairment) to 1 (severe impairment).

The AQLQ(S) +12 change in total score from baseline at Week 28 and Week 52 is calculated for all participants.

4.2.10.2 Derivations

The total score is calculated as the mean response to all questions. The 4 individual domain scores (4 domains assessing: symptoms, activity limitations, emotional function, and environmental stimuli) are the means of the responses to the questions in each of the domains. Higher scores indicate better outcomes. The following are the question numbers on the AQLQ(S) +12 questionnaire relating to each domain:

Table 6 AQLQ(S) +12 domains

Domain	AQLQ(S) +12 question number
Symptoms	6, 8, 10, 12, 14, 16, 18, 20, 22, 24, 29, 30
Activity Limitations	1, 2, 3, 4, 5, 11, 19, 25, 28, 31, 32
Emotional Function	7, 13, 15, 21, 27
Environmental Stimuli	9, 17, 23, 26

If response to any of the questions is missing, the AQLQ(S) +12 total score is automatically set to missing. If response to a question within a domain is missing, the score for that domain is automatically set to missing. It is directly managed at the data entry level.

The absolute change from baseline in AQLQ(S)+12 total score and in each domain at a post-baseline visit are calculated as described in Section 3.3 on the FAS. Baseline value is derived as presented in Section 3.3.1.2. Strategies of handling intercurrent events are presented in Section 4.2.

4.2.10.3 Handling of Dropouts and Missing Data

No data imputation.

4.2.10.4 Primary Analysis of Secondary Endpoint

The absolute values and absolute changes from baseline in total AQLQ(S)+12 score and in each domain are summarised using descriptive statistics over time. All data available at primary DBL is presented, which includes data beyond Week 28 (see Section 3.1).

The same statistical analysis as described in Section 4.2.7.4 is applied for the absolute change from baseline in total AQLQ(S)+12 score. The baseline of total AQLQ(S)+12 score is used as covariate instead of the baseline OCS.

The analyses are performed based on the FAS.

4.2.10.5 Additional Analyses of Secondary Endpoint

No additional analysis.

4.2.10.6 Subgroup Analyses of Secondary Endpoint

The analysis described in Section 4.2.10.4 is repeated in subgroups described in Section 4.2.1.7 for the absolute change from baseline in AQLQ(s)+12 total score.

4.2.10.7 Interim Analysis of Secondary Endpoint

No presentation for interim analysis.

4.2.11 Secondary Endpoint - Change from baseline in St. George's Respiratory Questionnaire (SGRQ) total score at Week 28 and Week 52

4.2.11.1 Definition

The SGRQ is a 50-item PRO instrument developed to measure the health status of participants with airway obstruction diseases. The questionnaire is divided into 2 parts: part 1 consists of 8 items pertaining to the severity of respiratory symptoms in the preceding 4 weeks; part 2 consists of 42 items related to the daily activity and psychosocial impacts of the individual's respiratory condition. The SGRQ yields a total score and 3 domain scores (symptoms, activity and impacts). The total score indicates the impact of disease on overall health status. This total score is expressed as a percentage of overall impairment, in which 100 represents the worst possible health status and 0 indicates the best possible health status. Likewise, the domain scores range from 0 to 100, with higher scores indicative of greater impairment.

The St. George's Respiratory Questionnaire (SGRQ) total score change from baseline at Week 28 and Week 52 is calculated for all participants. The change from baseline is also calculated for each of the 3 domains.

4.2.11.2 Derivations

Absolute change from baseline in SGRQ total score and for each domain at a post-baseline visit are calculated as described in Section 3.3 on the FAS. Baseline value is derived as presented in Section 3.3.1.2. Strategies of handling intercurrent events are presented in Section 4.2.

If response to any of the questions is missing, the SGRQ total score is automatically set to missing. If response to a question within a domain is missing, the score for that domain is automatically set to missing. It is directly managed at the data entry level.

4.2.11.3 Handling of Dropouts and Missing Data

No data imputation.

4.2.11.4 Primary Analysis of Secondary Endpoint

The absolute values and absolute changes from baseline in SGRQ total score and in each domain are summarised using descriptive statistics over time. All data available at primary DBL is presented, which includes data beyond Week 28 (see Section 3.1).

The same statistical analysis as described in Section 4.2.7.4 is applied for the absolute change from baseline in SGRQ total score. The baseline of SGRQ total score is used as covariate instead of the baseline OCS. In addition, the model for primary DBL at Week 28 does not include visit as a covariate as well as participant is not included in the REPEATED statement (i.e., ANCOVA model).

The analyses are performed based on the FAS.

4.2.11.5 Additional Analyses of Secondary Endpoint

No additional analysis.

4.2.11.6 Subgroup Analyses of Secondary Endpoint

The analysis described in Section 4.2.11.4 is repeated in subgroups described in Section 4.2.1.7 for the absolute change from baseline in SGRQ total score.

4.2.11.7 Interim Analysis of Secondary Endpoint

No presentation for interim analysis.

4.2.12 Exploratory Endpoint - Changes from baseline in biomarker levels at Week 28 or Week 52

4.2.12.1 Definition

The changes from baseline in biomarker (EOS, FeNO, IgE) levels at Week 28 or Week 52 is calculated for all participants in the FAS.

4.2.12.2 Derivations

The absolute changes from baseline in biomarker (EOS, FeNO, IgE) levels at a post-baseline visit are calculated as described in Section 3.3 on the FAS. Baseline value is derived as presented in Section 3.3.1.2. Strategies of handling intercurrent events are presented in Section 4.2.

4.2.12.3 Handling of Dropouts and Missing Data

No data imputation.

4.2.12.4 Primary Analysis of Exploratory Endpoint

The absolute values and changes from baseline in biomarker levels are summarised using descriptive statistics over time on the FAS. All data available at primary DBL is presented, which includes data beyond Week 28 (see Section 3.1).

4.2.12.5 Additional Analyses of Exploratory Endpoint

No additional analysis.

4.2.12.6 Subgroup Analyses of Exploratory Endpoint

No subgroup analysis.

4.2.12.7 Interim Analysis of Exploratory Endpoint

The absolute values and changes from baseline in biomarker levels, derived as described in Section 4.2.12.2, are summarised over time on the FAS.

4.2.13 Exploratory Endpoint - Time to 50% and 100% reduction of OCS dose over Week 28 and Week 52

4.2.13.1 Definition

The time to reach 50% and 100% OCS dose reduction from baseline over Week 28 and Week 52 is presented for all participants in the FAS.

4.2.13.2 Derivations

The derivation of baseline OCS maintenance dose is defined in Section 3.3.1.2. The OCS dose in mg/day is derived using therapy reasons given in Section 3.3. The percent change from baseline in OCS dose/day is calculated as presented in Section 3.3 on the FAS. Strategies of handling intercurrent events are presented in Section 4.2.

The time (in days) from first IP dose to achieve 50% reduction of OCS dose for the 1st time are calculated as follows:

Time to 50% OCS reduction (days) = (Date of 50% OCS reduction from baseline achieved for the 1^{st} time – date of IP dose) + 1.

If there is no sufficient OCS dose reduction (i.e. percentage OCS dose reduction < 50%) during 28 (or 52) weeks or prior to initiation of another biologic, participants are censored at earliest[date of Visit 9/Week 28 if available or date of first IP dose +196 days if visit not done (or date of the Visit 15/Week 52 if available or date of first IP dose + 364 days if visit not available), date of initiation of another biologic].

The Time to 100% OCS reduction (days) is calculated using the same approach described for the 50% OCS reduction on the FAS.

4.2.13.3 Handling of Dropouts and Missing Data

No data imputation.

4.2.13.4 Primary Analysis of Exploratory Endpoint

Number and percentages of participants who achieved OCS reduction thresholds (for both 50% and 100%) are summarised at Week 28 and Week 52.

Time to OCS reductions is analysed using the Kaplan-Meier estimates. A Kaplan-Meier plot is presented as well as summary tables including adjusted median time to event along with 95% confidence interval calculated using the Kaplan-Meier estimate respectively for 50% and 100% OCS reduction thresholds until Week 28 and Week 52.

The analyses are performed based on FAS.

4.2.13.5 Additional Analyses of Exploratory Endpoint

No additional analysis.

4.2.13.6 Subgroup Analyses of Exploratory Endpoint

No subgroup analysis.

4.2.13.7 Interim Analysis of Exploratory Endpoint

The derivation of baseline, post-baseline and change from baseline in daily maintenance OCS dose is described in Section 4.2.7.2. The time (in days) to achieve 50% or 100% reduction of OCS dose for the 1st time is derived as presented in Section 4.2.13.2.

The results are presented as described in Section 4.2.13.4.

Exploratory Endpoint - Proportion of participants with normal, partial, complete AI at Week 28 and Week 52

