The same visit window definitions are used regardless of whether the planned treatment period or the on-treatment period is used for analysis. Each data record in the planned treatment period is first identified, and then further flagged as on-treatment if applicable. This flag is used to select all eligible records for subsequent visit windowing, according to whether the derived visits are to be used in a planned treatment period or an on-treatment period analysis. It should be noted that, if treatment was discontinued within a particular visit window, the rules above for handling two values within the same visit window could select a different record according to whether a planned treatment period analysis or an on-treatment period analysis is needed.

Table 3 summarises the visit windows to be used. "4-weekly Visit Window" corresponds to the 4-weekly protocol scheduling for clinic visits, including those variables which are not captured at every clinic visit, unless otherwise stated. Sparse visit windows are defined also for specific parameters not measured every 4 weeks.

The 4-weekly visit window approach is replaced by a weekly based approach for ACQ-6 measured weekly. For Week 1, the window is [2; 11] and then for each week, the window is defined as (Target day for Week X - 3; Target day for Week X + 3), where Target day for Week X = (Week number * 7) + 1. For example: Target day for Week 10 is 71 (i.e., 10*7+1) and the visit window is (68 - 74).

Visit windows presented in Table 3 does not apply for calculation of daily OCS dose at each timepoint. The OCS dose at each visit is based on actual visit dates to account for changes in OCS dose at scheduled visit. The visit window at Week X is calculated as [Visit(X-1) date + 2 days; Visit(X) date + 1 day]. For Week 52, the visit window is [Visit 14 date + 2 days; Visit 15 date].

Table 3. Adjusted analysis Visit Windowing

Visit	Time	Target	4-weekly Visit	Spar	Sparse Visit Window			
	Point	Day	Window	(Sparse CSP sch		edule)		
				AQLQ	SGRQ/ PPOCS/ SNOT-22	AIRQ		
Visit 2	Week 0	1	NA	NA	NA	NA		
Visit 3	Week 4	29	2 - 42	2-56	-	-		
Visit 4	Week 8	57	43 - 70			-		
Visit 5	Week 12	85	71 - 98	-	-	-		
Visit 6	Week 16	113	99 - 126	-	-	-		
Visit 7	Week 20	141	127 - 154	-	-	-		
Visit 8	Week 24	169	155 - 182	-	-	-		
Visit 9	Week 28	197	183 - 210	169-224	169-224	-		
Visit 10	Week 32	225	211 - 238	-	-	-		
Visit 11	Week 36	253	239 - 266	-	-	-		
Visit 12	Week 40	281	267 - 294	-	-	-		

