5 INTERIM ANALYSIS

An interim analysis may be performed if approximately 50 participants complete V4 before a data cut-off date planned on mid-April 2023. All data available for participants who completed Visit 4 prior to the data cut-off date will be included. The results are not used to change any element of the study design and the study continues regardless of the results of interim analysis.

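### The censoring rule reused for the interim time-to-OCS-reduction analysis has no data cut-off term, so cumulative reduction, mainly 100% reduction, is underestimated after about Day 57

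*SAP*

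**What the plan says.** SAP section 5 admits to the interim analysis anyone past Visit 4 (Week 8) at a cut-off planned for mid-April 2023: "All data available for participants who completed Visit 4 prior to the data cut-off date will be included". About 50 participants are expected. SAP 4.2 acknowledges that their follow-up is shorter than Week 28 and that the OCS endpoints must be adapted for this.

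For time to 50% and 100% reduction, SAP 4.2.13.7 redirects the dose derivation to 4.2.7.2, but for the event time it states "The time (in days) to achieve 50% or 100% reduction of OCS dose for the 1st time is derived as presented in Section 4.2.13.2". It takes the presentation from 4.2.13.4: a Kaplan-Meier plot and a median with 95% CI, to Week 28 and to Week 52.

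SAP 4.2.13.2 censors a participant without sufficient reduction at the earlier of two dates. One is the start of another biologic. The other is, for Week 28, "date of Visit 9/Week 28 if available or date of first IP dose +196 days if visit not done" and, for Week 52, "date of the Visit 15/Week 52 if available or date of first IP dose + 364 days if visit not available". The 100% endpoint "is calculated using the same approach described for the 50% OCS reduction on the FAS".

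**The concern.** At the interim cut-off some participants will be ongoing, without the event and short of Visit 9. The rule assigns them a censoring date that can lie after the cut-off. The Kaplan-Meier estimator then keeps them in the risk set over days on which nothing has been observed, and treats those days as event-free. The denominators are too large, so the estimated probability of having reached the reduction is too low. If the event-free curve is plotted instead, it is too high; the SAP does not say which is drawn. The median moves later or is not reached.

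These participants have not withdrawn or died, so a withdrawal or death term would not cure this. The missing element is the data cut-off. Protocol 9.5 gives publication as the purpose of the interim analysis, so an error here could reach readers.

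**Working it through.** **Day count.** SAP 4.2.13.2 counts days as a date difference plus one ("date of IP dose) + 1"), so first dose + 196 days is Day 197 and + 364 days is Day 365. This agrees with SAP 3.3.2 ("Target day for Week X = (Week number * 7) + 1"): 28 × 7 + 1 = 197 and 52 × 7 + 1 = 365. Visit 4 has target Day 57. A participant without the event who is at Day 57 on the cut-off date therefore gains 197 − 57 = 140 unobserved days at risk, or 365 − 57 = 308 under the Week 52 rule.

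**What the estimator becomes.** If nobody leaves the risk set before Day 197, 1 − KM is simply the number of events seen so far divided by n. Illustration (assumed): 50 participants, follow-up spread evenly over Days 57 to 196, true probability 50% by Day 197. One such data set has 17 events by the cut-off.

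- SAP rule: 1 − KM at Day 196 = 17/50 = 0.34.
- Censored at the cut-off: 0.46.
- Days at risk without data: 2612, against 5228 observed person-days.

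**When events can occur.** Stepping through Protocol Table 7 without interruption, first reduction at Week 4:

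- 100% reduction: Week 8 (Day 57) from 5 mg; Week 16 (Day 113) from 10 mg (7.5, 5, 2.5 and 0 mg at Weeks 4, 8, 12 and 16); Week 20 (Day 141) from 20 mg.
- 50% reduction: Day 29 from 5 mg; Day 43 from 15 or 20 mg; Day 50 from 30 or 40 mg; Day 57 from 7.5, 10 or 25 mg; Day 71 from 12.5 mg.

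So 100% events fall largely after the minimum interim follow-up, and 50% events largely at or before it.

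**Constant-hazard simulation (assumed).** n = 50, 2000 replicates, no event before Day 29, hazard λ = −ln(1 − p)/168 so that the true probability by Week 28 is p. Follow-up at cut-off is uniform from Day 52 (Visit 4 target less 5 days) to the stated maximum. Entries are truth / SAP rule.

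| p | Max Day 113, read at Day 100 | Max Day 197, read at Day 183 | Max Day 365, read at Day 196 |
|---|---|---|---|
| 0.3 | 0.142 / 0.104 | 0.280 / 0.180 | 0.300 / 0.247 |
| 0.5 | 0.257 / 0.193 | 0.472 / 0.318 | 0.500 / 0.415 |
| 0.7 | 0.403 / 0.310 | 0.671 / 0.473 | 0.700 / 0.596 |
| 0.9 | 0.627 / 0.501 | 0.880 / 0.685 | 0.900 / 0.802 |

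Subtracting gives shortfalls of about 4 to 13, 10 to 20 and 5 to 10 points. Censoring at the cut-off stays within 1 point of the truth in every cell. At Day 56 the two rules agree (0.111 each for p = 0.5, maximum Day 197). For p = 0.7 the median moves from Day 125 to not reached (maximum Day 197) or to Day 135 (maximum Day 365). For p = 0.9 and maximum Day 197 it moves only from Day 79 to Day 81.

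**Later events, closer to 100% reduction (assumed).** Event day = 85 + gamma (shape 2, mean 40 or 30 days), with 65% or 80% ever reaching it; follow-up uniform from Day 57. At Day 196:

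- Follow-up to Day 197: 0.63 true against 0.34 (29 points), and 0.79 against 0.46 (33 points). The median is lost in both.
- Follow-up to Day 300: 0.64 against 0.47 (17 points), and 0.79 against 0.61 (18 points).

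**50% reduction (assumed).** Events from Day 29 (gamma shape 2), 80% reach it, follow-up uniform over Days 57 to 197. At Day 196 the truth is 0.80; the SAP rule gives 0.79 with a mean delay of 15 days and 0.77 with 25 days. The shortfall is 1 to 3 points and the median is unaffected. Slow tapers can raise it to about 14 points.

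**The case against.** The best counter-argument is that the SAP is silent rather than wrong. The rule in 4.2.13.2 addresses people without sufficient reduction over 28 or 52 weeks whose visit was not done. Someone at Day 60 has not had 28 weeks, and Visit 9 is not due. SAP 4.2 says OCS endpoints must be adapted, and section 5 limits the interim to data available at the cut-off, so a sensible programmer would censor there. This does not remove the gap. Read that way, ongoing participants have no defined censoring date at all. Section 5 governs which data enter, not where follow-up ends. The one cut-off statement in the period definitions (SAP 3.3.1.1) is confined to the primary database lock.

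Other parts of the counter-case stand. A reader might infer that both the 50% and the 100% medians would be lost; the taper timing shows that the 50% result is usually little affected. A reader might infer that most of the interim sample is misclassified, or take one scenario as the size of the bias. Accrual appears nowhere in the documents, and the share of participants falsely kept at risk in the constant-hazard runs ranged from 0.14 to 0.89. A reader might also infer that a wrong curve has been published. Protocol 9.5 speaks of key efficacy and safety objectives, nothing says this exploratory plot is among the published results, and the documents do not say whether the interim was run.

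**Conclusion.** The point holds as a minor defect. As written, the interim censoring date can fall after the data cut-off, and the cumulative probability of reduction is then underestimated beyond the shortest follow-up, about Day 57. The direction is certain wherever such participants exist. The size is not: for 100% reduction it is about 4 to 20 points under a constant hazard and about 17 to 33 points at Day 196 with events starting at Day 85; for 50% reduction it is usually 1 to 3 points. All of these depend on assumed accrual and event timing.

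The consequence is limited. The endpoint is exploratory, the interim is optional with about 50 participants, no hypothesis is tested and the results cannot change the design. The Week 28 and Week 52 analyses are not the subject of this point.

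**What to change.** In SAP 4.2.13.7 state that, for the interim analysis, participants without the event are censored at the earliest of the 4.2.13.2 censoring date and the data cut-off date, and that curves and medians are shown only over the follow-up available. The cut-off date is preferable to the last recorded OCS dose date, which may precede the cut-off by weeks for someone on a stable dose, depending on how the record is dated.

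The cost is one or two sentences and no new data. However, the planned mid-April 2023 cut-off precedes SAP edition 5.0 (9 November 2023), so editing the text may only document an analysis already done. If the interim was run, the sponsor should verify the censoring actually programmed and, if it followed 4.2.13.2 literally, correct any output.
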